5.2.2 Known Potential Benefits

There is no guaranteed benefit to study participants; however, based on EB-P12-01, we expect to observe benefits including substantially decreased SARS-CoV-2 virus in the upper respiratory tract and quicker resolution of COVID-19 signs and symptoms. Use of EmitBio™ RD-X19 is intended to reduce SARS-CoV-2 viral load and alleviate the clinical signs and symptoms associated with COVID-19. There is also the potential for benefit to society resulting from insights gained from participation in this, and other similar studies

6 STUDY DESIGN

The study population is individuals confirmed infected with an FDA-authorized SARS-CoV-2 antigen test who have mild to moderate COVID-19. Study subjects must be symptomatic for 72 hours or less and have a positive COVID-19 antigen test within the past 24 hours of screening.

The targeted number of subjects randomized per Cohort in the dose finding portion of the study is 30 individuals seronegative for SARS-CoV-2 Spike IgG antibodies (minimum 60 subjects total, with sponsors option to increase enrollment by an additional 150 total subjects to include all serostatuses after a dose has been selected based on safety for the final cohort). Based on findings in the EB-P12-01 and the hazard ratio observed for the median time to sustained symptom resolution in the proof of concept trial, the increased sample size with an anticipated roughly equal number of antibody positive to negative individuals in the final cohort has at least 90% power in the modified full analysis set population to detect clinically meaningful changes in SARS-CoV-2 symptom resolution (Hazard ratio of 0.4 between active RD-X19 and Sham observed in EB-P12-01).

The target population in the full analysis set (FAS) for the Final Cohort will reflect the underlying communities largely impacted by COVID-19, possessing both seropositive and seronegative individuals from a mixture of vaccinated and unvaccinated subjects, and with a high prevalence of circulating variants. Nasopharyngeal and saliva biospecimens collected at baseline may be analyzed to obtain genetic sequencing and characterize the incidence of SARS-CoV-2 variants in the study population.

Subject Inclusion and Exclusion Criteria must be confirmed by a study clinician, licensed to make medical diagnoses.

6.1 Inclusion Criteria

A subject must meet all the following criteria to be eligible for **inclusion** in this study:

1. Positive for SARS-CoV-2 as detected using an FDA authorized SARS-CoV-2 antigen test at or within 24 hours of the screening visit.
2. COVID-19 signs and symptoms within 72 hours from symptom onset, including at least two moderate* or greater symptoms from: cough, sore throat, nasal congestion, headache, unexplained chills and/or sweats, myalgia, fatigue, nausea (with or without vomiting).
 - Subjects with the presence of at least one moderate symptom and either a) a fever with an oral temperature of at least 100.5 °F or b) shortness of breath/difficulty breathing on exertion (e.g., walking, going up and down stairs) are also eligible for enrollment.
3. BMI <40
4. Provides written informed consent prior to initiation of any study procedures.

5. Be able to understand and agrees to comply with planned study procedures and be available for all study visits.
6. Agrees to the collection of saliva, nasopharyngeal, and venous blood specimens per protocol.
7. Males or females, 18 to 65 years of age, inclusive.
8. No uncontrolled disease process(es) based on patient reported medical history (chronic or acute), other than direct COVID-19 signs and symptoms.
9. No physical or mental conditions or attributes at the time of screening, which in the opinion of the PI, will prevent full adherence to, and completion of, the protocol.

*Symptom scoring is independent from the classification of COVID-19 disease severity at baseline. Guidance to study subjects for grading of signs and symptoms will be based on definitions used for the grading of TEAEs:

- None (Grade 0): Not present
- Mild (Grade 1): Symptoms that are usually transient and may require only minimal or no palliative or specific therapeutic intervention and generally do not interfere with the subject's usual activities of daily living.
- Moderate (Grade 2): Symptoms that are usually alleviated with palliative or specific therapeutic intervention. The symptoms interfere with usual activities of daily living causing discomfort but pose no significant or permanent risk of harm to the study subject.
- Severe (Grade 3): Events interrupt usual activities of daily living, or significantly effect clinical status, or may require intensive therapeutic intervention. Severe events are usually incapacitating.

6.2 Exclusion Criteria

A subject who meets any of the following criteria will be **excluded** from participation in this study:

1. Positive urine pregnancy test at screening or females who intend to become pregnant during the study.
2. COVID-19 signs associated with severe respiratory distress or imminent serious medical outcomes.^{^^}

^{^^}Potential Study Subjects Presenting with any of the following should be referred for immediate medical care and are not eligible for the study:

- Fever > 104° F
- Cough with sputum production

- Rales and/or rhonchi
- Difficulty breathing with respiratory distress defined by a respiratory rate ≥ 30 per minute, heart rate ≥ 125 per minute, $\text{SpO}_2 \leq 93\%$ on room air at sea level or $\text{PaO}_2/\text{FiO}_2 < 300$.
- Persistent pain or pressure in the chest
- Confusion

3. Any medical disease or condition that, in the opinion of the site Principal Investigator (PI) or appropriate sub-investigator, precludes study participation.
5. Reports a recent positive test result (within the past 6 months) for hepatitis A, hepatitis B or, hepatitis C virus antibody, or HIV-1 antibodies at screening.
6. Has a history of alcohol abuse or other recreational drug (excluding cannabis) use within 1 month of Study Day 1.
7. Currently enrolled in or plans to participate in another clinical trial with a therapeutic investigational agent (e.g., monoclonal antibody, oral protease inhibitor) that will be received during the study period.
8. History of systemic antiviral therapies (e.g., remdesivir) within the past 30 days.
9. History of oral or parenteral corticosteroid use within the past 30 days. Active use of nasal or inhalable steroids is also exclusionary. Topical steroids are not exclusionary.
10. Has a history of hypersensitivity or severe allergic reaction (e.g., anaphylaxis, generalized urticaria, angioedema, other significant reaction) to sun exposure.
11. Currently undergoing photodynamic therapy (PDT) or photochemotherapy (PUVA) for an unrelated disease or condition that utilizes photosensitizing drugs including but not limited to 5-aminolevulinic acid, methyl-5-aminolevulinic acid, porfimer sodium, methoxsalen (8-methoxysoralen), 5-methoxysoralen, trioxsalen.
12. Has any oral abnormality including ulcer, oral candidiasis, oral mucositis, gingivitis, burning mouth syndrome, a disease that can result in xerostomia (e.g. Sjogren's syndrome), or other oral disorder that in the opinion of the investigator would interfere with device use and evaluation.
13. Any intra-oral body piercings that cannot be removed and remain removed for the duration of the study. Metal orthodontia is permitted as braces will be covered by the device mouthpiece.
14. Any individual without teeth or with a dental malformation that precludes directed use of the device as intended.

6.3 Overall Design

Volunteers will provide written informed consent prior to initiating any screening procedures. Those meeting all screening criteria will be eligible for enrollment into the study. Study subjects

will be randomized in a 2:1 ratio within each Cohort, targeting to complete two cohorts in ascending or descending fashion based on safety/tolerability of Cohort A as follows:

Cohort A: RD-X19 24 J/cm² vs. Sham

(5 minute treatment, 2X/Day for a duration of 7 days)

Cohort B: RD-X19 32 J/cm² vs. Sham

(5 minute treatment, 2X/Day for a duration of 7 days)

Cohort C: RD-X19 16 J/cm² vs. Sham

(5 minute treatment, 2X/Day for a duration of 7 days)

Volunteers meeting all inclusion criteria and none of the exclusion criteria will be randomized in a 2:1 ratio within each cohort (30 per cohort). Assessments of study subjects will occur on study days 1, 3, 5, 8, with the final assessment visit on Day 14. Individuals who are hospitalized will be tracked until discharge or death and the date and time of these events will be captured in the study data.

This is a randomized, adaptive dose-finding study. The primary goal of the study is to evaluate multiple doses of the RD-X19 treatment device and establish evidence for safety and efficacy for a single selected RD-X19 doses compared to sham in SARS-CoV-2 infected individuals with outpatient COVID-19.

The primary efficacy outcomes are: (i) time to sustained symptom resolution in all patients (mild or moderate disease at baseline); and (ii) time to sustained symptom resolution in patients with mild disease at baseline. Other clinical and microbiological outcomes will also be assessed.

Since CMP and CBC results may not be available until study day 3, all volunteers who have significant clinical abnormalities will be immediately contacted and advised of the abnormality, discontinued from active participation in the protocol and advised regarding appropriate medical follow-up outside the study. All such study subjects will be replaced with a new volunteer.

Subjects who test positive for SARS-CoV-2 antibodies from blood draws at baseline will continue treatment for the duration of the study, undergo all assessments, and be excluded from the modified full analysis set (mFAS). For each subject testing positive for SARS-CoV-2 antibodies at baseline, one additional subject will be enrolled and randomized into the study for each of Cohorts A and B (*does not apply to optional enrollment period once the dose has been selected for the additional 150 subjects).

Safety and tolerability (local reactogenicity) will be assessed actively on each clinic visit by review of study subjects' daily diary cards for potential TEAEs, and oral cavity examination and targeted physical examination, as required.

Metabolic, liver, kidney and hematological laboratory evaluations will be performed at screening and at Day 14 or early termination (and potentially during unscheduled) clinic visits.

Subjects will be instructed to fill out diary cards twice daily to assess their symptoms associated with disease progression and record the number of treatments completed. Each of the eight symptoms will be rated on a 4-point scale from none (0) to severe (3) and a summary severity average will be calculated. Twice daily oral temperatures and oxygen saturation levels (SpO2) will also be recorded on the diary from readings taken by at-home devices dispensed to each subject. Reminders will be sent to each subject twice daily via an appropriate communication platform (e.g. text messaging).

Study Subject safety will be monitored throughout the study by the Investigator and supported by regular review by the Medical Monitor and a Chartered Safety Monitoring Committee.

6.4 Objectives and Outcome Measures

| OBJECTIVES | ENDPOINTS (OUTCOME MEASURES) |
|-----------------------------|--|
| Safety Assessments | 
• Serious Adverse Events (SAEs) and Treatment Emergent Adverse Events (TEAEs) characterized by Medical Dictionary for Regulatory Affairs (MedDRA) System Order Classified (SOC) Preferred Terms (PTs), including application site local reactions and device-related TEAEs 
• Collection and summary of all TEAEs reported from study subjects' daily diary cards or in office visits and via monitoring for application site reactions during clinic visits by investigators' examination of intraoral pathology. MedDRA SOC PT-defined TEAEs will be established and evaluated individually and collectively for severity and attribution and presented in tables and listings. |
| Primary Outcome Assessments | 
• Sustained resolution of COVID-19 signs and symptoms in all subjects (with mild or moderate disease at baseline) 
• Time to sustained resolution of COVID-19 signs and symptoms as measured by the time (in hours) when cough, sore throat, nasal congestion, headache, chills and or sweats, myalgia, fatigue, and nausea (with or without vomiting) have been assessed by the subject as none (0) or mild (1) and all symptoms remain at or below 1 until study Day 14. |

| | |
|---|---|
| | 
*Subjects reporting a persistent fever (100.5 degrees for 36 hours or more) and/or SpO₂ levels <96% with any shortness of breath fail to meet the success criterion on that day even if all other symptoms are reported as none (0) or mild (1).
 |
| 
Sustained resolution of COVID-19 signs and symptoms in subjects with Mild disease at baseline | 
Time to sustained resolution of COVID-19 signs and symptoms as measured by the time (in hours) when cough, sore throat, nasal congestion, headache, chills and/or sweats, myalgia, fatigue, and nausea (with or without vomiting) have been assessed by the subject as none (0) or mild (1) and all symptoms remain at or below 1 until study Day 14. 
*Subjects reporting a persistent fever (100.5 degrees for 36 hours or more) and/or SpO₂ levels <96% with any shortness of breath fail to meet the success criterion on that day even if all other symptoms are reported as none (0) or mild (1).
 |
| Secondary Clinical Outcome Assessments | |
| 
Day 8 Composite Resolution | 
Proportion of study subjects who achieve 'Day 8 Composite Resolution' is defined as both a negative SARS-CoV-2 antigen test within the window for Visit 4 and all symptoms assessed by the subject as none (0) or mild (1), absence of fever and SpO₂ ≥96% without shortness of breath on study day 8. |

| | |
|--|--|
| 
• Worsening of Disease• Return to Pre-COVID Health• Severe Clinical Outcomes | 
• Number and percentage of study subjects who experience progression of COVID-19 as defined by an increase of the composite COVID-19 severity score greater than baseline at any point in the study on or after day 3.• Numbers and percentages of study subjects on day 8 and day 14 who answer Yes to the following patient-reported global impression assessments, a) return to usual health and b) return to usual activities.
a) In the past 24 hours, have you returned to your usual health (before your COVID-19 illness)? Yes or Nob) In the past 24 hours, have you returned to your usual activities (before your COVID-19 illness)? Yes or No• Numbers and percentages of study subjects who:
1) who require medical attention or intervention attributed to COVID-19;2) who progress to severe disease with respiratory rate >30/minute and/or O2 saturation <94% on room air or FiO2 ≥300% with any respiratory distress;3) who require hospitalization for severe COVID-19;4) who require endotracheal ventilation or ECMO with or without the use of solumedrol; and5) who die. |
| Secondary Virologic Outcome Assessments | |
| 
• Change in Nasopharyngeal VL | 
• Mean change in nasopharyngeal VL from baseline on days 3, 5, 8, and 14.• Tabulated geometric mean |

| | |
|---------------------------------------|---|
| | 
nasopharyngeal VL at baseline and on Days 3, 5, 8 and 14.
 
• Clearance of viral shedding (undetectable SARS-CoV-2 VL) |
| 
Exploratory Assessments
 | |
| | 
• Change in oral microbiome• Change in saliva VL 
• Change in α and β diversity in microbial flora from baseline on day 8 and day 14 as analyzed by 16S rRNA subunit analysis from frozen saliva samples.• Mean change in saliva VL on days 3, 5, 8, and 14.• Tabulated geometric mean saliva VL at baseline and on days 3, 5, 8 and 14. |

The study SAP will outline all study analytical tables and listings, by treatment assignment and whether analysis population is Safety/FAS, mFAS or PP.

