| | 
• Day 8 Composite Resolution• Worsening of Disease• Return to Pre-COVID Health 
• Proportion of study subjects who achieve 'Day 8 Composite Resolution' defined as both a negative SARS-CoV-2 antigen test within the window for Visit 4 and all symptoms assessed by the subject as none (0) or mild (1), absence of fever and SpO₂ ≥96% without shortness of breath on study day 8.• Number and percentage of study subjects who experience progression of COVID-19 as defined by an increase of the composite COVID-19 severity score greater than baseline at any point in the study on or after day 3.• Numbers and percentages of study subjects on day 8 and day 14 who answer yes to the following patient-reported global impression assessments, a) return to usual health and b) return to usual activities.
a) In the past 24 hours, have you returned to your usual health (before your COVID-19 illness)? Yes or Nob) In the past 24 hours, have you returned to your usual activities (before your COVID-19 illness)? Yes or No• Numbers and percentages of study subjects who: |

| | |
|--|--|
| 
• Severe Clinical Outcomes | 
1) who require medical attention or intervention attributed to COVID-19;2) who progress to severe disease with respiratory rate >30/minute and/or O2 saturation $\leq 93\%$ on room air or FiO2 $\geq 300\%$ with any respiratory distress;3) who require hospitalization for severe COVID-19;4) who require endotracheal ventilation or ECMO with or without the use of solumedrol; and5) who die. |
| Secondary Virologic Outcome Assessments | |
| 
• Change in Nasopharyngeal VL• Clearance of viral shedding (undetectable SARS-CoV-2 VL) | 
• Mean change in nasopharyngeal VL from baseline on days 3, 5, 8, and 14.• Tabulated geometric mean nasopharyngeal VL at baseline and on Days 3, 5, 8 and 14.• Proportion of subjects demonstrating clearance of viral infection, defined as a negative nasopharyngeal swab via RT-qPCR as assessed on each of Days 3, 5, 8 and 14. |
| Exploratory Assessments | |
| 
• Change in oral microbiome | 
• Change in α and β diversity in microbial flora from baseline on day 8 and day 14 as analyzed by 16S rRNA subunit analysis from frozen saliva |

| | |
|---|--|

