 - Subjects will be instructed to fill out diary cards twice daily to assess their symptoms associated with disease progression and record the number of treatments completed. Each of the eight symptoms will be rated on a 4-point scale from none (0) to severe (3). Temperature and oxygen saturation will also be measured and recorded via devices provided by site personnel and taken home by the subject. Subjects will also be asked if they experience any shortness of breath. Reminders will be sent to each subject twice daily via an appropriate communication platform (e.g. text messaging) and up to date diary cards should be presented at each clinical visit to be eligible for subject payments. Between visits on Days 2 and 4, to enhance safety monitoring and reinforce adherence to at-home study procedures, each subject will be contacted via phone and verbally go through diary procedures and document any AEs.
- Severe COVID-19 Clinical Outcomes
 - There is a small amount of risk that subjects with mild-to-moderate COVID-19 may have an unknown health problem or co-morbidity at the time of screening that can lead to rapid worsening of condition or hospitalization during study. Worsening of condition will be characterized by study subjects who experience COVID-19 progression defined by an increase of the composite COVID-19 severity score greater than baseline at any point in the study on or after day 3.

- Medically attended visits as a result of severe COVID-19 clinical outcomes will be aggregated into the following categories:
 - 1) those who require medical attention attributed to COVID-19;
 - 2) those who progress to severe disease with respiratory rate >30/minute and/or O2 saturation ≤93% on room air or FiO2 ≥300% with any respiratory distress;
 - 3) those who require hospitalization for severe COVID-19;
 - 4) those who require endotracheal ventilation or ECMO with or without the use of solumedrol; and
 - 5) those who die.
- Subjects with a primary care, urgent care, or emergency room visit that are not hospitalized as a result of their medical consultation, may continue treatment with the investigational device and should attend regularly scheduled follow up visits per protocol. Subjects that are admitted to the hospital should discontinue all treatment in lieu of standard of care for severe/critical COVID-19 illness.

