  - b) In the past 24 hours, have you returned to your usual activities (before your COVID-19 illness)?
- Proportion of study subjects with any one or more of the following severe clinical outcomes (including proportions of study subjects for each individual outcome):

- 1) who require medical attention or intervention attributed to COVID-19
- 2) who progress to severe systemic illness with respiratory rate  $\geq 30$ /minute, heart rate  $\geq 125$ , O2 saturation  $\leq 93\%$  on room air or PaO2/FiO2  $\leq 300$  mm Hg, or lung infiltrates upon imaging  $>50\%$ .
- 3) who require hospitalization for severe COVID-19
- 4) who require endotracheal ventilation or ECMO with or without the use of solumedrol
- 5) who die

Secondary virologic endpoints:

- Mean change in nasopharyngeal viral load on days 3, 5, 8, and 14
- Geometric mean nasopharyngeal viral load at baseline and on days 3, 5, 8, and 14
- Proportion of subjects demonstrating clearance of viral infection, defined as a negative nasopharyngeal swab via RT-qPCR as assessed on Days 3, 5, 8 and 14

Exploratory assessments of effects of RD-X19 in saliva viral load include:

- Mean change in saliva viral load on days 3, 5, 8, and 14
- Geometric mean saliva viral load at baseline and on days 3, 5, 8, and 14

Exploratory assessment of effects of RD-X19 in oral microbiome includes:

- Change in  $\alpha$  and  $\beta$  diversity in microbial flora from baseline on day 8 and day 14 as analyzed by 16S rRNA subunit analysis from frozen saliva samples

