	-- n (%) subjects who require hospitalization for severe COVID-19	XX (XX.X)	XX (XX.X)	XX (XX.X)	XX (XX.X)
	-- n (%) subjects who require endotracheal ventilation or ECMO	XX (XX.X)	XX (XX.X)	XX (XX.X)	XX (XX.X)
	-- n (%) subjects who die	XX (XX.X)	XX (XX.X)	XX (XX.X)	XX (XX.X)
Modified Full Analysis Set					
	N	XX	XX	XX	XX
	n (%) Subjects who experience progression of COVID-19 	XX (XX.X)	XX (XX.X)	XX (XX.X)	XX (XX.X)
	n (%) Subjects with severe clinical outcomes (at least one of following)	XX (XX.X)	XX (XX.X)	XX (XX.X)	XX (XX.X)
	-- n (%) subjects who require medical attention or intervention attributed to COVID-19	XX (XX.X)	XX (XX.X)	XX (XX.X)	XX (XX.X)
	-- n (%) subjects who progress to severe disease 	XX (XX.X)	XX (XX.X)	XX (XX.X)	XX (XX.X)
	-- n (%) subjects who require hospitalization for severe COVID-19	XX (XX.X)	XX (XX.X)	XX (XX.X)	XX (XX.X)
	-- n (%) subjects who require endotracheal ventilation or ECMO	XX (XX.X)	XX (XX.X)	XX (XX.X)	XX (XX.X)
	-- n (%) subjects who die	XX (XX.X)	XX (XX.X)	XX (XX.X)	XX (XX.X)
Per Protocol Population					
	N	XX	XX	XX	XX
	n (%) Subjects who experience progression of COVID-19 	XX (XX.X)	XX (XX.X)	XX (XX.X)	XX (XX.X)
	n (%) Subjects with severe clinical outcomes (at least one of following)	XX (XX.X)	XX (XX.X)	XX (XX.X)	XX (XX.X)
	-- n (%) subjects who require medical attention or intervention attributed to COVID-19	XX (XX.X)	XX (XX.X)	XX (XX.X)	XX (XX.X)
	-- n (%) subjects who progress to severe disease 	XX (XX.X)	XX (XX.X)	XX (XX.X)	XX (XX.X)
	-- n (%) subjects who require hospitalization for severe COVID-19	XX (XX.X)	XX (XX.X)	XX (XX.X)	XX (XX.X)
	-- n (%) subjects who require endotracheal ventilation or ECMO	XX (XX.X)	XX (XX.X)	XX (XX.X)	XX (XX.X)
	-- n (%) subjects who die	XX (XX.X)	XX (XX.X)	XX (XX.X)	XX (XX.X)

[1]: Progression of COVID-19 is defined by increase of composite COVID-19 severity score (> baseline score) at any point in the study on or after Day 3.

[2]: Subjects will be designated as Severe having any one of the following: Respiratory Rate  $\geq 30$ , Heart Rate  $\geq 125$ , SpO2  $\leq 93\%$ , or lung infiltrates upon imaging  $>50\%$ .

EmitBio Inc.  
Protocol: EB-P20-01  
SAP Version: 2.0

Source: Listing 16.x.x  
O:\Studies\EmitBio\EB-P20-01\Biometrics\Programs\Tables\xxx.sas ran on Month Day, Year at hh:mm on data from Month Day, Year.

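### Progression to severe disease is defined by three non-equivalent rules, and the protocol's rule contains an FiO2 limb that cannot be met

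*Protocol*

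**What the plan says.** Both documents list five severe clinical outcomes as a secondary endpoint. Item 2 is progression to severe disease.

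- **Protocol 6.4:** a respiratory rate above 30 per minute "and/or O2 saturation <94% on room air or FiO2 ≥300% with any respiratory distress".
- **Protocol 9.2:** "those who progress to severe disease with respiratory rate >30/minute and/or O2 saturation ≤93% on room air or FiO2 ≥300% with any respiratory distress". The Objectives and Outcome Measures table in Protocol 4.1.2 (Table 1) uses the same thresholds as 9.2.
- **SAP 3.2:** subjects "who progress to severe systemic illness with respiratory rate" ≥30 per minute, heart rate ≥125, oxygen saturation ≤93% on room air, PaO2/FiO2 ≤300 mm Hg, or lung infiltrates >50% on imaging.
- **SAP Table 14.2.2.3, footnote 2:** "Subjects will be designated as Severe having any one of the following: Respiratory Rate" ≥30, heart rate ≥125, SpO2 ≤93%, or infiltrates >50%. There is no PaO2/FiO2 limb.

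SAP 3.2 also defines an overall row, "Proportion of study subjects with any one or more of the following severe clinical outcomes", and asks for the proportion with each individual outcome as well. Item 1 of the five is medical attention or intervention attributed to COVID-19, with no severity threshold.

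Elsewhere the protocol uses PaO2/FiO2 below 300 as a sign of severe illness (exclusion criterion 2 in 4.2 and 6.2, the severity categories in Section 7, and the proposed indication in 8.1.2).

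**The concern.** An endpoint component needs one rule that a programmer can apply to the data. Here the protocol, the SAP text and the SAP table shell can each give a different count for the same row from the same dataset, and two of the three rules sit inside the SAP itself.

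The protocol's oxygenation limb cannot work as written. It appears in three sections, so it is not a slip in one place.

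At stake is the item 2 row and, through it, the overall row. Hospitalisation, ventilation or ECMO, and death do not depend on these thresholds.

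**Working it through.** The documents give no rate, power or alpha for this endpoint, so there is no planned figure to reproduce. The check is to write each text as a logical rule and apply the rules to the same hypothetical subjects. RR is respiratory rate, HR heart rate and P/F the PaO2/FiO2 ratio.

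**Rules**
- Protocol endpoint (4.1.2, 6.4, 9.2), with the FiO2 limb read literally and the distress phrase attached only to that limb: RR >30 or SpO2 ≤93%. The FiO2 limb adds nobody, because a fraction of inspired oxygen cannot exceed 100%. For whole-number oximeter readings, <94% and ≤93% are the same, so the 6.4 wording is not counted as a separate rule.
- SAP 3.2: RR ≥30, or HR ≥125, or SpO2 ≤93%, or P/F ≤300, or infiltrates >50%.
- SAP footnote: RR ≥30, or HR ≥125, or SpO2 ≤93%, or infiltrates >50%.

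**Profiles.** These are assumptions chosen to test one limb at a time. Every value not named stays below all thresholds, and there is no respiratory distress unless stated.

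| Only abnormal finding | Protocol endpoint | SAP 3.2 | SAP footnote |
|---|---|---|---|
| RR exactly 30 | not severe | severe | severe |
| HR 130 | not severe | severe | severe |
| Infiltrates 60% | not severe | severe | severe |
| P/F 280 | not severe | severe | not severe |
| P/F exactly 300 | not severe | severe | not severe |
| RR 31 | severe | severe | severe |
| SpO2 93% | severe | severe | severe |

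The first three rows separate the protocol from the SAP. The fourth and fifth separate the two SAP texts. There are therefore three distinct rules.

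**If the FiO2 limb was meant as a ratio.** Read as P/F ≥300 with any respiratory distress, it runs opposite to the <300 in Protocol 4.2, 6.2, 7 and 8.1.2 and to the ≤300 in SAP 3.2. A subject with P/F 400 and some distress would be severe under the protocol endpoint and not severe under either SAP rule.

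**The distress phrase.** The protocol wording does not settle whether respiratory distress qualifies every limb or only the last. If it qualifies every limb, the last two rows of the table (RR 31 and SpO2 93%, each without distress) become not severe under the protocol and stay severe under the SAP.

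**An internal contrast on respiratory rate.** Exclusion criterion 2 and Section 7 place a rate of exactly 30 on the severe side, while the protocol endpoint does not.

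**The case against.** The strongest reply is that little depends on this. All secondary endpoints are descriptive (SAP 5.5.2), and hypothesis testing is confined to the two primary endpoints (Protocol 10.1). The schedule of activities contains no blood gas and no imaging, so ratio and infiltrate data could come only from outside care, and the footnote omission should rarely change a classification. SAP Section 6 also says the shells may be modified. All of this stands and limits the impact. It does not remove the mismatch: respiratory rate and heart rate are measured at every clinic visit, and those limbs differ between protocol and SAP.

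Stronger readings are tempting, and the documents do not support them.

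- *A reader might infer that the overall severe-outcomes row makes the endpoint useless because it mostly counts consultations.* No rate of medical attention is given. As an illustration on assumed rates, suppose 5% to 10% of 174 subjects need medical attention (8.7 to 17.4), 1% to 2% meet items 2 to 5 (1.7 to 3.5), and the latter all lie within the former. The non-severe share then runs from 1 − 3.5/8.7, about 60%, to 1 − 1.7/17.4, about 90%. That range reflects the assumptions. The 174 (98 + 76) is the example count used for alpha in SAP 5.1.1 and is not the denominator of any column in Table 14.2.2.3. In the earlier 31-subject trial, Protocol 4.1 reports no medical intervention beyond over-the-counter self-medication. Medical attention is also the protocol's own item 1, and the SAP already gives each component its own row.
- *A reader might infer that the SAP drops a respiratory-distress condition.* That holds only if the phrase qualifies every protocol limb, which the wording leaves open.
- *A reader might take Section 7 as the ready-made single definition.* It is a severity category that requires symptoms as well as signs, and it introduces the signs as examples. Adopting it would also choose a clinical rule, which is for the sponsor.

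**Conclusion.** The inconsistency is real. One secondary endpoint component has three non-equivalent definitions: one in the protocol, one in the SAP text and one in the SAP table footnote. The protocol's version includes a condition that no subject can meet. This conclusion rests on the wording alone and on the fact that FiO2 cannot exceed 100%; the profiles in the check only show where the rules part.

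The number of subjects affected cannot be derived from the documents. The consequence is confined to the item 2 row and the overall row of a descriptive table, and no test or power statement depends on either.

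Separately, the overall row includes medical attention with no severity threshold, so it should not be read as a rate of severe COVID-19. The component rows already planned serve that purpose.

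**What to change.** Before unblinding:

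1. Put one identical definition of progression to severe disease in Protocol 4.1.2 (Table 1), 6.4 and 9.2, SAP 3.2, and footnote 2 of SAP Table 14.2.2.3. The sponsor chooses the thresholds and which limbs to include; this review does not say which are right.
2. Correct or remove the FiO2 ≥300% limb. If a ratio was intended, state it as PaO2/FiO2, with the direction and boundary reconciled across the documents.
3. State whether the respiratory-distress phrase applies to every limb or only to the last.
4. When reporting, describe the overall row as at least one of the five listed outcomes, including medical attention, and draw statements about severe COVID-19 from the component rows.

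The cost is wording in the protocol and the SAP. No new data are needed and the primary analysis is unaffected. Counts in the item 2 row and the overall row may change, depending on the definition chosen.
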